- To assess the safety and reactogenicity of the 1790GAHB vaccine in terms of solicited adverse events, unsolicited adverse events, serious adverse events (SAEs), adverse events of special interest (AESI) and laboratory parameters.
- To assess safety after challenge in terms of SAEs, unsolicited adverse events, AESI, and laboratory parameters.

205626 (S SONNEI MONO GMMA SBVGH-003 [H03_03TP])
Protocol Amendment 6 Final

Immunogenicity

- To evaluate the IgG ELISA immunogenicity profile of the 1790GAHB vaccine at 7 days and 28 days after the first and second vaccination (IgG ELISA coated with OAg containing LPS).
- To evaluate the immunogenicity profile of the 1790GAHB vaccine at pre-challenge and at 7 and 28 days after challenge (IgG ELISA coated with OAg containing LPS).
- Number and percentage of seroresponders for anti-*S. sonnei* LPS at 28 days after first and second vaccination.
- To assess anti- *S. sonnei* LPS concentration ≥ 121 EU/ml at 28 days after first and second vaccination.

Tertiary

The following tertiary objectives, which are part of the study exploratory objectives may be evaluated in addition to the primary and secondary objectives and will complement assessment of the vaccine immunogenicity profile:

- Evaluate *S. sonnei* specific secretory immunoglobulin A (sIgA) in stool at Day 1 and 7 days after first and second vaccination and 7 days after challenge (Day 64).
- Evaluate *S. Sonnei LPS IgG-specific* α4β7+/plasmablast *response* at Day 1 and 7 days after first and second vaccination and 7 days after challenge (Day 64). (*Amended: 23 July 2019*)
- Evaluate serum bactericidal activity against *S. sonnei* at Day 1 and 28 days after first and second vaccination.
- Evaluate correlation between serum anti-*S. sonnei* LPS IgG level, serum bactericidal activity titer, shigellosis, shedding, mild, moderate, severe or more severe diarrhea, and dysentery after challenge.
- Evaluate glycosylation of fragment crystallisable (Fc) portion of IgG antibodies at Day 1 and 28 days after second vaccination and association with clinical protection and/or serological endpoints.
- Evaluate inflammatory response from stools collected before challenge at Visit 5 (Day 57) and daily, post challenge, during inpatient stay (Day 57 to Day 64).

205626 (S SONNEI MONO GMMA SBVGH-003 [H03_03TP])
Protocol Amendment 6 Final

- Evaluate gene expression signatures at Day 1 and 7 days after first and second vaccination and 7 days after challenge (Day 64).

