- Number and percentage of subjects that show correlation between serum anti-*S. sonnei* LPS IgG concentration, serum bactericidal activity titer, shigellosis, shedding, moderate to severe diarrhea (MSD), dysentery and mild diarrhea after challenge.
- Concentration of stool markers of intestinal inflammation (e.g. calprotectin and myeloperoxidase) before oral challenge with S. sonnei, 53G at Visit 5 (Day 57) and daily during the inpatient stay after challenge administration (Day 57 to Day 64).
- The number of differential expressed genes 7 days after first and second vaccination and 7 days after challenge by comparing the relative abundance of mRNA sequences compared to Day 1 (prevaccination baseline).
- Diversity and frequency of microbiome components (taxa and/or genes according to technology) at Day 1 prior to vaccination and 28 days after second vaccination (Visit 5; Day 57).

Exploratory analysis for hypotheses generation will include the evaluation of the association of the microbiome components with efficacy and immunogenicity described above.

205626 (S SONNEI MONO GMMA SBVGH-003 [H03_03TP]) Protocol Amendment 6 Final

TABLE OF CONTENTS

			PAGE
SP	ONSO	R INFORMATION	7
SYI	NOPSI	S	8
LIS	T OF A	ABBREVIATIONS (AMENDED: 23 JULY 2019)	31
GL	OSSAF	RY OF TERMS	34
TR	ADEM A	ARKS	39
1.	INTRO	ODUCTION	40
•	1.1.	Background	
	1.2.	Rationale for the study and study design	

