Microbiome analysis in stool will be done using 16s ribosomal deoxyribonucleic acid (DNA) amplicon sequencing and/or shotgun whole genome sequencing. These will use DNA sequencing to identify the bacteria and their genes present in the sample to explore associations to immunogenicity and challenge outcome. Shotgun sequencing might generate subject's DNA sequence information; however, these sequences are filtered out and will not be analyzed. Depending on the results of the microbiome analysis, additional follow-up studies might include microbiome gene expression profiling (ribonucleic acid sequencing or another method), culture and functional characterization of the bacteria in the sample in animal models.

Fecal markers of intestinal inflammation will be measured as a sensitive predictor for inflammatory activities in the gastrointestinal tract. This analysis will assess if concentrations of inflammatory markers such as calprotectin and myeloperoxidase will increase after oral challenge with *S. sonnei* 53G and will additionally investigate if the *S. sonnei* 1790GAHB vaccine can reduce or abrogate the inflammatory response in the intestine after oral challenge.

Gene expression will be studied using high-throughput technologies (including but not limited to RNAseq or microarrays) measuring the relative abundance of RNA molecules in PBMCs harvested at several timepoints following vaccination and challenge. Computational analysis will subsequently identify pathways and biological themes associated with vaccination and acute disease and transcriptional patterns may be related to metadata including humoral and cellular responses to vaccination.

^{*}Chemistry performed only at screening unless required for subject management

^{**}GVGH laboratory refers to the GVGH-laboratories in Siena, Italy

205626 (S SONNEI MONO GMMA SBVGH-003 [H03_03TP])
Protocol Amendment 6 Final

Additional exploratory testing on the vaccine and/or on the disease under study may be performed within the framework of the study if deemed necessary for accurate interpretation of the data or should such assay(s) become available at GSK. These assays may not be represented in the objectives/endpoints of the study protocol.

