11.3. Tertiary endpoints

- Specific anti-S. sonnei LPS sIgA antibody concentration in stool samples at Day 1, 7 days after first and second vaccination and 7 days after challenge (Day 64).
- Frequency of *S. sonnei* LPS specific IgG α4β7+/- antibody secreting cells per 10⁶ PBMC plasmablast at Day 1 and 7 days after first and second vaccination and 7 days after challenge (Day 8, Day 36 and Day 64). (*Amended: 23 July 2019*)
- Glycosylation profiles of IgG antibodies at Day 1 and 28 days after second vaccination (Visit 5; *Day 57*).
- Number and percentage of subjects that show correlation between serum anti-*S. sonnei* LPS IgG concentration, SBA titer, shigellosis, shedding, MSD, dysentery and mild diarrhea after challenge.
- Concentration of stool markers of intestinal inflammation (e.g. calprotectin and myeloperoxidase) before oral challenge with *S. sonnei*, 53G at Visit 5 (Day 57) and daily during the post-challenge inpatient stay (Day 57 to Day 64).
- The number of differential expressed genes 7 days after first and second vaccination and 7 days after challenge by comparing the relative abundance of mRNA sequences compared to Day 1 (pre-vaccination baseline).
- Diversity and frequency of microbiome components (taxa and/or genes according to technology) at Day 1 prior to vaccination and 28 days after second vaccination (Visit 5; Day 57).

Exploratory analysis for hypotheses generation will include the evaluation of the association of the microbiome components with efficacy and immunogenicity described above.

205626 (S SONNEI MONO GMMA SBVGH-003 [H03_03TP])
Protocol Amendment 6 Final

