11.4. Determination of sample size

Primary objective - Efficacy

In comparing the protective efficacy of 1790GAHB vaccine against the placebo group the following assumptions will be made:

Assuming a true VE of 70%, a total number of 21 confirmed cases will be needed to demonstrate that the LL of the two-sided 90% CI for the VE is above 0% with 80% power (by Pass 2013, One Proportion Power Analysis, one-sided test, one-sided alpha = 5%).

Based on the results obtained by the Cincinnati Children's Hospital Medical Center, where the challenge model was developed, in subjects receiving a challenge with 1500 CFU of *S. sonnei* 53G, the attack rate for the primary case definition of this study is 58%. Thus considering an AR of 58% in the placebo group and a percentage of non-evaluable subjects of 22%, approximately 72 subjects (36 per group) will be recruited to reach these 21 cases.

The assumption on the value of true VE is based on the percentage of subjects with seroresponse observed in previous studies where the 1.5/25 µg OAg/protein dose of 1790GAHB vaccine was evaluated. In the phase I study in Europe, the observed percentage of subjects with seroresponse was 63% and 88% after 1st and 2nd vaccination respectively. In the Phase IIa study, conducted in endemic region, the observed percentage of subjects with seroresponse was 68% and 90% after 1st and 2nd vaccination, respectively.

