- qPCR: S. sonnei qPCR determination will be done following the SOPs of the local or designated laboratory for identification of *S. sonnei* by a qPCR from stool specimens.
- S. sonnei sIgA and total sIgA determination from stool: S. Sonnei ELISA will be performed following the SOPs of the local or designated laboratory for ELISA assay from stool specimens. The S. sonnei sIgA result will be normalized to the total sIgA.

Stool inflammatory markers assay

Inflammatory markers including calprotectin and myeloperoxidase levels in stools (ng/mL) will be measured using commercially available (Epitope Diagnostics, Inc.) quantitative ELISA kits according to the manufacturer's instructions.

α4β7 plasmablast ELISA (Amended: 23 July 2019)

Anti-S. sonnei LPS-specific IgG titers will be determined in plasmablasts, in both $\alpha 4\beta 7$ positive and $\alpha 4\beta 7$ negative populations. The titers provided will be measured by ELISA assay in the culture supernatant of $5x10^6$ cells, by using an in-house method developed in WRAIR. (Amended: 23 July 2019)

Transcriptomics

The transcriptomics signals analysis will be performed evaluating the number of differential expressed genes by comparing the relative abundance of mRNA sequences.

Gut Microbiome profile:

Gut microbiome analysis in stool using 16s ribosomal DNA amplicon sequencing and/or shotgun whole genome sequencing (refer to Section 6.7.3).

205626 (S SONNEI MONO GMMA SBVGH-003 [H03_03TP])
Protocol Amendment 6 Final

Glycosylation profiles of IgG antibodies:

The activity of IgG antibody is mediated through two functional domains, the Fab and the Fc. The Fc domain mediates effector functions though specific interactions with FcγRs expressed on the surface of leukocytes, and activation of diverse immunomodulatory pathways impacting both innate and adaptive immunity [1]. The mechanisms of Fc domain diversification that determine Fc-FcγR interaction include IgG subclass and Fc-associated glycan structure [2]. Distinct profiles are enriched following vaccination or during inflammatory diseases or infection. Vaccination with 1790GAHB is hypothesized to enrich certain IgG subclasses and Fc glycan structures and specific profiles of elicited IgG will contribute to clinical protection observed in controlled human infection models.

References for Appendix A:

- 1. Bournazos S and Ravetch JV. Fcγ receptor pathways during active and passive immunization. Immunol Rev. 2015; 268:88-103.

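### The gene-expression endpoint is a count of genes differing from Day 1 with no contrast to placebo, so it cannot attribute change to the vaccine.

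*Protocol*

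**What the plan says.** The Synopsis (Endpoints, Tertiary) and Section 11.3 define the endpoint in the same terms: "The number of differential expressed genes 7 days after first and second vaccination and 7 days after challenge", obtained "by comparing the relative abundance of mRNA sequences compared to Day 1 (pre-vaccination baseline". Appendix A repeats the metric: "The transcriptomics signals analysis will be performed evaluating the number of differential expressed genes by comparing the relative abundance of mRNA sequences". Section 12.9 also speaks only of a number of genes. The comparator is fixed as Day 1, and no study arm is named in any of these places.

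The matching objective (Section 2.3) is to evaluate gene expression signatures at Day 1, 7 days after each vaccination and 7 days after challenge. Section 6.7.3 says what is wanted from the data: "Computational analysis will subsequently identify pathways and biological themes associated with vaccination and acute disease". It adds that transcriptional patterns may be related to humoral and cellular responses.

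Placebo samples are part of the plan. Table 11 lists transcriptomics for all 72 enrolled subjects at Visits 1, 2 and 4 and at Day 64. There is no such sample at Day 57, just before challenge.

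**The concern.** Section 6.7.3 wants pathways associated with vaccination. A change from Day 1 within subjects shows that something changed, not that the vaccine changed it. Randomisation supplies the comparison that separates the two, and the endpoint does not use it.

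Tabulating the count for each arm would not fully repair this. Two arms with the same count may share every gene or none, so counts cannot be subtracted to give a vaccine effect.

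A count is also a poor measure of response size. If a gene is called different when a test passes a significance limit, the endpoint is a number of rejected tests and rises with the number of paired samples even when the biology is unchanged.

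At stake is the reading of an exploratory result: changes common to both arms could be reported as a vaccine signature.

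**Working it through.** **1. What both arms share at each sampling day.**

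- Days 8 and 36: an intramuscular injection containing aluminium (Table 13 gives 0.7 mg aluminium per mL for the vaccine formulation and for the placebo), elapsed time and processing batch.
- Day 64: the same, plus the *S. sonnei* 53G challenge on Day 57 (both arms, Table 14) and antibiotics from Day 62 or earlier (Section 3.2). With no Day 57 sample for this assay, the Day 64 change from Day 1 mixes vaccination, challenge and treatment. Only the placebo arm can isolate the vaccine's part.

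**2. The vaccine adds nothing beyond placebo.** Assumptions, none from the protocol: 12,000 independent genes; 10% shifted by 0.6 SD of the paired difference in both arms alike; 36 pairs per arm; paired t-tests; Benjamini-Hochberg at 5%.

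- Count against Day 1, vaccine arm: about 856 genes.
- Genes flagged by testing the vaccine-minus-placebo difference in change: about 0.1.

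**3. Dependence on the number of pairs, if genes are called by significance.** The protocol gives no figure for the expected count, so there is none to reproduce. Two effect models, both with paired t-tests and Benjamini-Hochberg at 5%:

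| Assumed effects | 36 pairs | 28 pairs | Reduction |
|---|---|---|---|
| Fixed 0.5 SD, 10% of 12,000 genes | 493 | 223 | (493 − 223)/493 = 55% |
| Fixed 0.6 SD, 10% of 12,000 genes | 854 | 559 | (854 − 559)/854 = 35% |
| Normal, SD 0.3, 20% of 15,000 genes | 277 | 136 | (277 − 136)/277 = 51% |
| Normal, SD 0.5, 20% of 15,000 genes | 1014 | 786 | (1014 − 786)/1014 = 22% |
| Normal, SD 0.8, 20% of 15,000 genes | 1719 | 1524 | (1719 − 1524)/1719 = 11% |

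At a fixed 0.8 SD the reduction is 10% to 11%. The range is therefore about 10% to 55%.

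**4. Two arms, identical true change, correlated genes** (4,000 genes, 20% changed, effect SD 0.5, 60 runs).

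- 36 v 36 pairs: mean counts 269 v 272, median absolute gap about 20 genes.
- 36 v 28 pairs: mean counts 273 v 220, median absolute gap 61 genes.
- Direct test between arms: mean 0 and 0.5 genes flagged, median 0 in both settings.

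**5. Where 28 comes from.** Section 11.4 assumes "a percentage of non-evaluable subjects of 22" percent: 36 × 0.78 = 28.1 per arm, and 28.1 × 0.58 × (1 + 0.30) = 21.2, the 21 cases required. The 22% thus belongs to the primary efficacy calculation. It is used here only as a convenient size of loss, not as an expected loss of blood samples.

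**The case against.** The case for leaving the text alone has five parts.

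- **Silence on arms is not a decision to ignore placebo.** Other tertiary endpoints in Section 11.3 name no arm either, and a statistical analysis plan could add the contrast. That is fair, and a reader should not infer that placebo data will go unused. What stands is narrower: here the protocol itself fixes both a metric and a comparator, and that pair cannot attribute change to vaccination.
- **No rule for calling a gene different is given.** Correct, and such a rule is commonly left to the analysis plan. The dependence on pairs is therefore conditional; a pure fold-change rule would behave differently. The attribution problem does not depend on the rule.
- **No comparison of counts across visits or arms is planned.** Also correct. A reader might infer that a lower count at Day 64 than at Day 8 will be presented as a biological change. Nothing in the protocol proposes this, and Section 11.11 makes such comparisons descriptive and not for interpretation.
- **The protocol does not expect these samples to fall from 36 to 28 per arm.** This stands. Table 11 plans 72 subjects at each of the four visits, and the 22% concerns efficacy evaluability.
- **Replacing the change from Day 1 altogether would do harm.** This stands too. Both arms are challenged, and a vaccine-minus-placebo difference removes the shared challenge response that the acute-disease signature needs. The contrast should be added, not substituted.

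**Conclusion.** The point holds in limited form. As worded, the endpoint counts change from Day 1 and contains no contrast with placebo, so it cannot support a statement about pathways associated with vaccination. This follows from the text and the design, needs no assumption about effect sizes, and holds with equal numbers in both arms.

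The dependence on sample number is a second, conditional weakness. Its size, about 10% to 55% between 36 and 28 pairs, rests on significance-based calling and on assumed effects. At the planned 36 v 36, two arms with the same biology give nearly equal mean counts.

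This is a cheap improvement. The endpoint is tertiary, Section 2.3 says only that it may be evaluated, and no primary or secondary conclusion is affected.

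**What to change.** In Section 11.3 and the Synopsis:

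- Add, as the main vaccine-related summary, the vaccine-minus-placebo difference in change from Day 1 at Days 8, 36 and 64, by gene and by pathway, with effect sizes and values adjusted for the false discovery rate (FDR).
- Keep the within-arm change from Day 1, including Day 64 in placebo subjects, for the acute-disease signature.
- Report any gene count by arm with its number of pairs, and do not compare counts across arms or visits with different numbers.

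Align the transcriptomics text in Appendix A and Section 12.9 with this.

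Cost: wording and some extra analysis, with no new samples or assays. The two-arm contrast has more variance than a one-arm before-after change, so fewer genes will pass the FDR limit.

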205626 (S SONNEI MONO GMMA SBVGH-003 [H03_03TP]) Protocol Amendment 6 Final

LIST OF ABBREVIATIONS (Amended: 23 July 2019)

AE: Adverse Event

AESI: Adverse Event of Special Interest

AR: Attack Rate

CCHMC: Cincinnati Children's Hospital Medical Center (USA)

CDC: Centers for Disease Control and Prevention

CFU: Colony Forming Units

CHIM: Controlled Human Infection Model

CI: Confidence Interval

CMI: Cell-Mediated Immunity

DNA: Deoxyribonucleic acid

eCRF: electronic Case Report Form

ELISA: Enzyme-linked immunosorbent assay

EoS: End of Study

EU: ELISA unit

FAS: Full Analysis Set

Fc: Fragment crystallisable

FDA: Food and Drug Administration, United States of America

GCP: Good Clinical Practice

GMC: Geometric Mean Concentration

GMMA: Generalized Modules for Membrane Antigens

GMR: Geometric Mean Ratio

GSK: GlaxoSmithKline

GVGH: GSK Vaccines Institute for Global Health

HCG: Human Chorionic Gonadotropin

205626 (S SONNEI MONO GMMA SBVGH-003 [H03_03TP])
Protocol Amendment 6 Final

HIV: Human Immunodeficiency Virus

HLA: Human Leukocyte Antigen

IB: Investigator Brochure

ICF: Informed Consent Form

ICH: International Council for Harmonisation

ID: Intradermal

IDMC: Independent Data Monitoring Committee

IEC: Independent Ethics Committee

IgG: Immunoglobulin G

IM: Intramuscular

IMP: Investigational Medicinal Product

IN: Intranasal

IRB: Institutional Review Board

LL: Lower Limit

LPS: Lipopolysaccharide

LSLV: Last Subject Last Visit

MACDP: Metropolitan Atlanta Congenital Defects Program

MedDRA: Medical Dictionary for Regulatory Activities

MSD: Moderate to Severe Diarrhea

OAg: O antigen

PBMC: Peripheral Blood Mononuclear Cells

PCD: Primary Completion Date

PPS: Per-Protocol Set

qPCR: quantitative Polymerase Chain Reaction

S. sonnei: Shigella sonnei

205626 (S SONNEI MONO GMMA SBVGH-003 [H03_03TP]) Protocol Amendment 6 Final

SAE: Serious Adverse Event

SBA: Serum Bactericidal Assay

SBIR: Source DataBase for Internet Randomization

SDB: Source Document Verification

sIgA: Secretory Immunoglobulin A

SPM: Study Procedures Manual

TMP-SMX: Trimethoprim-sulfamethoxazole

TSA: Trypticase soy agar

VE: Vaccine Efficacy

WRAIR: Walter Reed Army Institute of Research

205626 (S SONNEI MONO GMMA SBVGH-003 [H03_03TP])
Protocol Amendment 6 Final

GLOSSARY OF TERMS

Adequate contraception:

Adequate contraception is defined as a contraceptive method with failure rate of less than 1% per year when used consistently and correctly and when applicable, in accordance with the product label for example:

- Abstinence from penile-vaginal intercourse, when this is their preferred and usual lifestyle,
- Combined estrogen and progesterone oral contraceptives,
- Injectable progestogen,
- implants of etonogestrel or levonorgestrel,
- Contraceptive vaginal ring,
- Percutaneous contraceptive patches,
- Intrauterine device or intrauterine system,
- Male partner sterilization prior to the female subject's entry into the study, and this male is the sole partner for that subject,

The information on the male sterility can come from the site personnel's review of the subject's medical records; or interview with the subject on her medical history.

• Male condom combined with a vaginal spermicide (foam, gel, film, cream or suppository), and/or progesterone alone oral contraceptive.

Adequate contraception does not apply to subjects of childbearing potential with same sex partners, or for subjects who are and will continue to be abstinent from penile-vaginal intercourse on a long term and persistent basis, when this is their preferred and usual lifestyle.

Any untoward medical occurrence in a patient or clinical investigation subject, temporally associated with the use of a medicinal product, whether or not considered related to the medicinal product.

An adverse event (AE) can therefore be any unfavorable and unintended sign (including an abnormal laboratory finding), symptom, or disease (new or exacerbated) temporally associated with the use of a medicinal product. For marketed medicinal products, this also includes failure to produce expected benefits (i.e. lack of efficacy), abuse or misuse.

Adverse event:

205626 (S SONNEI MONO GMMA SBVGH-003 [H03 03TP]) Protocol Amendment 6 Final

Adverse Event of Special Interest:

Adverse events of special interest (AESIs): are predefined (serious or non-serious) adverse events of scientific and medical concern specific to the product or program, for which ongoing monitoring and rapid communication by the investigator to the sponsor can be appropriate, because such an event might warrant further investigation in order to characterize and understand it.

Blinding:

A procedure in which one or more parties to the trial are kept unaware of the treatment assignment in order to reduce the risk of biased study outcomes. The level of blinding is maintained throughout the conduct of the trial, and only when the data are cleaned to an acceptable level of quality will appropriate personnel be unblinded or when required in case of a serious adverse event. In an observer-blind study, the subject and the site and sponsor personnel involved in the clinical evaluation of the subjects are blinded while other study personnel may be aware of the treatment assignment (see Section 6.2.3 for details on observer-blinded studies).

Eligible: Qualified for enrolment into the study based upon strict

adherence to inclusion/exclusion criteria.

End of Study: For studies without collection of human biologicals samples or imaging data EoS is the last subject last visit (Synonym of End of Trial)

(LSLV).

For studies with collection of Human Biologicals Samples or imaging data, EoS is defined as the date of the last testing/reading released of the Human Biological Samples or imaging data, related to primary and secondary endpoints. EoS must be achieved no later than 8 months after LSLV.

An epoch is a set of consecutive timepoints or a single timepoint from a single protocol. Epochs are defined to support a main purpose which is either to draw conclusions on subject participation or to draw a complete conclusion to define or precise the targeted label of the product. Supporting means that data collected at the timepoints included in an epoch must be sufficient to fulfil the purpose of the epoch.

Typical examples of epochs are screening, primary vaccinations, boosters, yearly immunogenicity followups, and surveillance periods for efficacy or safety.

GSK's tracking tool for clinical trials.

Epoch:

eTrack:

205626 (S SONNEI MONO GMMA SBVGH-003 [H03 03TP]) Protocol Amendment 6 Final

Immunological correlate of protection:

The defined immune response above which there is a high

Investigational vaccine:

likelihood of protection in the absence of any host factors that might increase susceptibility to the infectious agent.

(Synonym of Investigational Medicinal Product)

A pharmaceutical form of an active ingredient being tested in a clinical trial, including a product with a marketing authorization when used in a way different from the approved form, or when used for an unapproved indication, or when used to gain further information about an approved use.

Menarche:

Menarche is the onset of menses for the first time in a young female and is preceded by several changes associated with puberty including breast development and pubic hair growth. Menarche usually occurs within 1-2 years of breast development, the larche. However, a young female can become pregnant before her first menses. Thus, a conservative definition of non-childbearing potential in a pre-menarcheal female is a young female who has not yet entered puberty as evidenced by lack of breast development (palpable glandular breast tissue).

Menopause:

Menopause is the age associated with complete cessation of menstrual cycles, menses, and implies the loss of reproductive potential by ovarian failure. A practical definition accepts menopause after 1 year without menses with an appropriate clinical profile at the appropriate age e.g. > 45 years.

The International Council for Harmonisation (ICH) E15

Pharmacogenomics:

Guidance for Industry defines pharmacogenomics as Study of variation of DNA and RNA characteristics as related to drug or treatment response. Pharmacogenetics, which is a subset of pharmacogenomics, is "the study of variations in DNA sequence as related to drug response." Pharmacogenomic biomarkers include germline (host) DNA and RNA as well as somatic changes (e.g., mutations) that occur in cells or tissues. Pharmacogenomic biomarkers are not limited to human samples but include samples from viruses and infectious agents as well as animal samples. The term pharmacogenomic experiment includes both the generation of new genetic or genomic (DNA and/or RNA) data with subsequent analysis as well as the analysis of existing genetic or genomic data to understand drug or treatment response (pharmacokinetics, safety, efficacy or effectiveness, mode of action). Proteomic and metabolomic biomarker research are not pharmacogenomics.

205626 (S SONNEI MONO GMMA SBVGH-003 [H03_03TP])
Protocol Amendment 6 Final

Primary completion

date:

The date that the final subject was examined or received an intervention for the purpose of final collection of data for all primary outcomes, whether the clinical trial was concluded according to the pre-specified protocol or was terminated.

Protocol amendment:

The International Council for Harmonisation (ICH) defines a protocol amendment as: 'A written description of a change(s) to or formal clarification of a protocol.' GSK Biologicals further details this to include a change to an approved protocol that affects the safety of subjects, scope of the investigation, study design, or scientific integrity of the study.

Randomization:

Process of random attribution of treatment/schedule to subjects in order to reduce bias of selection.

Self-contained study:

Study with objectives not linked to the data of another

study.

Site Monitor:

An individual assigned by the sponsor who is responsible for assuring proper conduct of clinical studies at one or more investigational sites.

Solicited adverse event:

AEs to be recorded as endpoints in the clinical study. The presence/occurrence/intensity of these events is actively solicited from the subject or an observer during a specified post-vaccination follow-up period.

Study vaccine/product:

Any investigational vaccine/product being tested and/or any authorized use of a vaccine/ product /placebo as a reference or administered concomitantly, in a clinical trial that evaluates the use of an investigational

vaccine/product.

Subject:

Term used throughout the protocol to denote an individual who has been contacted in order to participate or participates in the clinical study, either as a recipient of the vaccine or as a control.

Subject number:

A unique number identifying a subject, assigned to each subject consenting to participate in the study.

Subset:

Selection of blood samples among all blood sample collected at given timepoint(s) for testing by specific

(Synonym of Immuno-

subset)

assay.

Treatment:

Term used throughout the clinical study to denote a set of investigational product(s) or marketed product(s) or placebo intended to be administered to a subject.

205626 (S SONNEI MONO GMMA SBVGH-003 [H03_03TP])

Protocol Amendment 6 Final

Treatment number: A unique number identifying a treatment to a subject,

according to treatment allocation.

Unsolicited adverse event:

Any AE reported in addition to those solicited during the clinical study. Also any 'solicited' symptom with onset outside the specified period of follow-up for solicited symptoms will be reported as an unsolicited adverse event.

205626 (S SONNEI MONO GMMA SBVGH-003 [H03_03TP])
Protocol Amendment 6 Final

TRADEMARKS

The following trademarks are used in the present protocol.

Note: In the body of the protocol (including the synopsis), the names of the vaccines/products and/or medications will be written without the superscript symbol TM or ® and in *italics*.

Trademarks not owned by the GSK group of companies

Alhydrogel (Brenntag Nordic A/S [Brenntag Biosector A/S])

Generic description

Aluminium Hydroxide, Hydrated, for Adsorption (Alhydrogel 2% - Ph.Eur.)

205626 (S SONNEI MONO GMMA SBVGH-003 [H03_03TP])
Protocol Amendment 6 Final

